4.1.3 Technical Success Analysis Set

This analysis set is defined as all subjects with a successful study device implant, (i.e. technical success). The 6-month closure success co-primary endpoint will be analyzed using this set, as will all other postprocedure measures or outcomes except technical success, procedure success, and all assessments of clinical success.

4.1.4 Per-Protocol Analysis Set

For per-protocol analysis, only subjects who had no major protocol deviations (PDs) will be included in the analyses. Major PDs are defined as PDs with a level of seriousness such that inclusion of the subject(s) would unacceptably bias analyses of the primary endpoints. An example of a major PD might be failure to satisfy eligibility criteria to a degree where the subject does not fit the underlying scientific model for the treatment. Per-protocol criteria may be applied to both the all enrolled subjects and the technical success analysis sets.

Protocol deviations that may be considered major and lead to exclusion of a subject from the per-protocol analysis set include: inclusion/exclusion criteria (eligibility) deviations; failure to obtain informed consent; and retention of more than one study device.

If necessary, per-protocol analysis sets will be used for additional analyses of the primary and secondary endpoints.

4.2 Timing of Analyses

4.2.1 Primary Endpoint Analysis

The primary endpoints analysis will be performed and submitted to FDA as a Pre-Market Approval (PMA) after 6-month follow-up is complete on the Pivotal Phase cohort.

4.2.2 Interim Analyses

An interim analysis of 30-day safety data on the Pivotal Phase cohort will be performed and submitted to FDA after 30-day follow-up is complete on all Pivotal Phase subjects. The purpose of this analysis and submission is to obtain approval to begin enrollment in the Continued Access Phase of the study. No formal statistical testing of study hypotheses is planned for this analysis.

CONFIDENTIAL INFORMATION

MD133254 Statistical Analysis Plan Template

Revision#: 1

Doc Type: GC

10 of 13

4.3 Primary Endpoints

4.3.1 Test Method

The co-primary endpoints are both subject-based binomial proportions. For Co-Primary Endpoint 1, 6-Month Closure Success, exact binomial testing at the one-sided 5% significance level will be performed against the performance goal (null hypothesis proportion). If the observed proportion is greater than the performance goal and the statistical test p-value is ≤ 0.05 , then the null hypothesis will be rejected in favor of the alternative hypothesis of acceptable performance. In addition, the 95% one-sided Clopper-Pearson confidence interval lower bound will be reported. Depending on the outcome of this test, Co-Primary Endpoint 2, Composite Clinical Success, will be tested by the same method.

4.3.2 Test Hierarchy for Multiplicity Control

The overall Type I error rate of 5% will be controlled for multiplicity by the following hierarchical testing structure:

1. Test $H_0^{Closure}$ at $\alpha = 0.05$.
2. If testing fails to reject $H_0^{Closure}$, then testing stops and $H_0^{Clinical}$ is as well not rejected.
3. If testing rejects $H_0^{Closure}$, then test $H_0^{Clinical}$ at $\alpha = 0.05$.

4.4 Secondary Endpoints

Secondary endpoints (subject-based unless otherwise specified) will be descriptive only; no formal statistical hypotheses will be tested. Secondary endpoints will be summarized at the specified time points using the descriptive statistics described above. No claims of statistical significance will be made based on secondary endpoint results. Any p-values from these tests will not be reported in labeling, but may be used for scientific presentations and manuscripts.

4.5 Adverse Events

All site-reported AEs will be MedDRA coded and grouped by MedDRA System/Organ Class (SOC) and by MedDRA Preferred Term within SOC. AEs will also be grouped by seriousness (SAE vs. nonserious AE), primary relationship (device, procedure, study medication, and unrelated) and timing of onset (procedure, pre- and postdischarge). AEs will be summarized as rates given by subject-based binomial proportions. The numerator will be the count of subjects who experienced one or more episodes of the AE of interest in the time period of interest. The denominator will be the count of subjects free of the AE of interest through the time period of interest and with sufficient clinical follow-up for the time period of interest, plus the count of subjects in the numerator. Unless otherwise specified for a particular endpoint measure, all enrolled subjects in the analysis set of interest will be considered evaluable and will contribute to the denominator.

4.6 Baseline Characteristics

Subject demographics, clinical history, risk factors, and pre-procedure defect characteristics will be summarized using descriptive statistics for continuous variables (mean, standard deviation, number of observations, minimum and maximum) and discrete variables (percentage and count/sample).

CONFIDENTIAL INFORMATION

MD133254 Statistical Analysis Plan Template

Revision#: 1

Doc Type: GC

4.7 Subgroup Analysis of Primary Endpoints

The primary endpoints will also be analyzed controlling for the following baseline covariates: age; sex; race and ethnicity.

4.8 Poolability of Investigative Sites

The data from all investigative sites will be pooled based on the assumption of clinical comparability: the sites used a common protocol; the sponsor adequately monitored the study to assure protocol compliance; and the data gathering and validation mechanisms were the same across all study sites.

Analyses to justify pooling will include the following:

- Each co-primary endpoint will be presented by site.
- An assessment of the poolability of the sites using a 2-by-(number of sites) contingency table of the primary outcome versus site. Fisher's Exact Test will be used to assess homogeneity. Sites with fewer than five subjects will be combined into one or more virtual sites based on geographic region, with the number of virtual sites dependent on the number of subjects represented by small sites (fewer than five subjects) and the geographic distribution of such sites. The maximum number of subjects in a combined, virtual site for this poolability analysis will be limited to 15 subjects.
- If the sites are found to be significantly heterogeneous with respect to the outcome (p-value ≤ 0.10), additional analyses will be conducted to assess differences between sites in baseline and procedural variables that might explain differences in the primary outcome.

4.9 Additional Analyses

4.9.1 Wire Frame Fracture

In order to assess possible harm to subjects due to wire frame fracture, an additional analysis involving co-primary outcomes as well as device-related adverse events will be conducted by stratifying subjects with and without frame fracture. To preserve the temporal relationship, only those events that had an onset date on or following the possible timing of frame fracture will be counted in the frame fracture subgroup.

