Study Duration	Total Study Duration: 5.5 years
Schedule of Events	
Screening Assessments (within 6 months of procedure)
 

• Physical exam

• Electrocardiogram (ECG)

• Echocardiogram (TTE or TEE)

 
Pre-Study Procedure (within 90 days of procedure)
 

• Echocardiogram (TTE)

 
Procedure
 

• Physical exam

• Stop-flow balloon sizing of defect

• Echocardiogram (TEE, TTE or ICE)

• Fluoroscopy

 
Pre-Discharge
 

• Electrocardiogram (ECG)

• Echocardiogram (TTE)

 
30 days and 6 months:
 

• Physical exam

• Electrocardiogram (ECG)

• Echocardiogram (TTE)

• Fluoroscopy (6 months for all Subjects)

 
Long-term follow-up at 12 months and 36 months included:
 

• Physical exam

• Electrocardiogram (ECG)

• Echocardiogram (TTE)

• Fluoroscopy (36 months for all Subjects)

 
A telephone follow-up occurred at 24 months

Additional Information	Echocardiography Core Lab, Independent Data Review Board (IDRB)

CONFIDENTIAL INFORMATION

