2.5 Study Endpoints

2.5.1 Primary Endpoints

Co-Primary Endpoint 1: 6-Month Closure Success is defined as a clinical residual defect status of occluded or clinically insignificant as determined by the Echo Core Lab at the 6-month evaluation among subjects with technical success.

Co-Primary Endpoint 2: Composite Clinical Success is evaluated at 6 months after index procedure among subjects with attempted study device closure and is defined as satisfying all of the following criteria:

1. Technical Success: Successful deployment and retention (at conclusion of index procedure) of a GORE® CARDIOFORM ASD Occluder
2. Safety Success:
 - Freedom from any Serious Adverse Event (SAE) related to the device or procedure, as adjudicated by the Independent Data Review Board (IDRB) through 30 days post-procedure
 - Freedom from device events (post-procedure embolization, device removal, or other device reintervention) from completion of the implant procedure through 6 months (180 days) post-procedure
3. Closure Success: A clinical residual defect status of occluded or clinically insignificant as determined by the Echo Core Lab at the 6-month evaluation.

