2.5.2 Secondary Endpoints

Technical Success: Successful deployment and retention of the study device at the conclusion of the index procedure

Procedure Success: Technical success and measured residual defect status of occluded, small, or moderate of the target ASD at conclusion of the index procedure

Long-term Closure Success: Closure success evaluated at 12 months and 36 months

Long-term Composite Clinical Success: Composite clinical success evaluated at 12 months and 36 months

CONFIDENTIAL INFORMATION

MD133254 Statistical Analysis Plan Template

[figure not shown]
[figure not shown]
[figure not shown]
Revision#: 1

Doc Type: GC

Safety Outcomes: The proportion of subjects experiencing one or more SAEs within 30 days post-index procedure, and the proportion of subjects experiencing a device event (embolization; device removal; reintervention after completion of index procedure) through 6 months, 12 months, and 36 months post-index procedure

Clinically Significant New Arrhythmia: In subjects without prior history of arrhythmia, any new arrhythmia (documented on ECG) requiring hospitalization, initiation of new long-term medical therapy (persisting > 45 days), or any post-index procedure cardioversion or intervention (pacemaker, ablation, etc.)

2.6 *Statistical Hypotheses*

CONFIDENTIAL INFORMATION

MD133254 Statistical Analysis Plan Template

Revision# 1

Doc Type: GC

2.7 *Sample Size Determination*

2.7.1 [REDACTED]

CONFIDENTIAL INFORMATION

[figure not shown]
MD133254 Statistical Analysis Plan Template

Revision#: 1

Doc Type: GC

A series of six horizontal black bars of varying lengths, each ending in a small white bracket on the right side. The bars are arranged vertically, with the longest bar at the top and the shortest at the bottom. The brackets are positioned at the end of each bar, pointing to the right.

2.7.2

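### The wire-frame-fracture harm analysis names no closure or defined device-event outcome beyond 6 months, so fractures arising after a clean 6-month film are judged only on device-related adverse events

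*SAP*

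**What the plan says.** SAP 4.9.1 sets out to examine whether frame fracture harms subjects. It names two sets of outcomes: "an additional analysis involving co-primary outcomes as well as device-related adverse events will be conducted by stratifying subjects with and without frame fracture". It adds a rule on timing: "only those events that had an onset date on or following the possible timing of frame fracture will be counted in the frame fracture subgroup".

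SAP 2.5.1 fixes every part of the co-primary endpoints at or before 6 months:
- Closure, in both endpoints, is "a clinical residual defect status of occluded or clinically insignificant as determined by the Echo Core Lab at the 6-month evaluation".
- Device events count "from completion of the implant procedure through 6 months (180 days) post-procedure".
- Related serious adverse events count "as adjudicated by the Independent Data Review Board (IDRB) through 30 days post-procedure".

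The Schedule of Events in the protocol summary places follow-up fluoroscopy at two visits: "Fluoroscopy (6 months for all Subjects" and "Fluoroscopy (36 months for all Subjects".

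Later outcomes are already defined. SAP 2.5.2 lists long-term closure, "Closure success evaluated at 12 months and 36 months", and device events through 6, 12 and 36 months, as secondary endpoints. Under SAP 3.5 the core lab reads the 12- and 36-month echocardiograms. SAP 2.2 follows implanted subjects to 36 months. Section 4.9.1 names none of these later endpoints.

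**The concern.** A harm analysis needs outcomes that can occur after the exposure. For a frame that is intact on the 6-month film and fractured on the 36-month film, the co-primary outcomes were essentially settled before the fracture could have happened. Such a subject enters the fracture stratum with a co-primary result that the fracture could not have changed.

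The onset rule sensibly prevents earlier events from being blamed on a later fracture. Combined with a 6-month outcome, however, it leaves a late-fracture subject almost no route to a co-primary failure, while failures in the no-fracture stratum count in full.

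That leaves device-related adverse events as the only named outcome able to register harm from a late fracture. Under SAP 4.5 these are site-reported. A residual shunt that the core lab sees on a 12- or 36-month echo need not be reported as an adverse event. SAP 3.3 states board adjudication of relatedness only through 30 days (arrhythmia events excepted), so later attribution to the device appears to rest on the site. A finding of no harm could then reflect the choice of outcome rather than the behaviour of the device.

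**Working it through.** Section 4.9.1 gives no figure to reproduce. The check is whether the windows overlap.

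**Inputs**
- 6-month visit: 180 ± 14 days, so days 166 to 194 (SAP 3.2).
- 12-month visit: 365 ± 60 days, so days 305 to 425 (SAP 3.2).
- 36-month visit: 1095 ± 60 days, so days 1035 to 1155 (SAP 3.2).
- Co-primary device-event window closes at day 180, and the related-SAE window at day 30 (SAP 2.5.1).
- Fluoroscopy at 6 and 36 months (protocol summary).

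**1. When a fracture first seen at 36 months could have occurred, given a clean 6-month film**

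Interval = day of 36-month film − day of 6-month film.
- On target: 1095 − 180 = 915 days.
- Shortest: 1035 − 194 = 841 days.
- Longest: 1155 − 166 = 989 days.

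**2. How much of that interval the co-primary outcomes cover**

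Device events: overlap = max(0, 180 − day of 6-month film).
- Film at day 180 or later: 0 days.
- Film at day 166: 180 − 166 = 14 days. As a share, the largest value is 14 / (1035 − 166) = 14 / 869 = 1.6%.

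Related SAEs: the window closed at day 30, so the overlap is 0.

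Closure: the 6-month echo can follow the 6-month film by at most 194 − 166 = 28 days, and only if the two are done at opposite ends of the window.

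**3. If the 6-month film is missing**

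Possible onset then runs from day 0. The device-event window covers 180/1155 = 15.6% to 180/1035 = 17.4% of the interval.

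**4. Effect on the comparison**

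Let L be the share of the fracture stratum with late fractures, p the co-primary failure proportion among its early fractures, and q the failure proportion without fracture. If the onset rule is applied to co-primary failures, late fractures contribute about zero, so the stratum shows about (1 − L) × p. It looks worse than the no-fracture stratum only if p > q / (1 − L). The documents give no value for L. As assumptions only:
- L = 0: p must exceed q, with no distortion.
- L = 0.25: p must exceed q / 0.75 = 1.33q.
- L = 0.50: p must exceed q / 0.50 = 2q.

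If the rule is not applied to co-primary failures, late fractures contribute results that predate the fracture and say almost nothing about harm.

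**5. Whether the existing later endpoints fall in the right place**

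The earliest 12-month visit (day 305) is after the latest 6-month film (day 194). The latest 12-month visit (day 425) is before the earliest 36-month film (day 1035). The 12-month echo therefore lies inside the possible-onset interval, and the 36-month echo lies at its end. A 12-month finding counts under the onset rule only if possible timing is taken from the start of the interval. The SAP does not say whether it means the last clean film, a midpoint or the first positive film.

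**The case against.** Four points on the other side carry weight.

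- **Adverse events run on.** A reader might infer that 4.9.1 cannot show late device events at all. The text does not support that. It includes device-related adverse events, sets no 6-month limit on them, and implanted subjects are followed to 36 months. A late embolization, removal or reintervention can appear if the site reports it as device-related. What is absent is the defined device-event endpoint and any later closure outcome.
- **Fractures seen at 6 months.** A reader might also infer that the 6-month echo says little about these because film and echo belong to the same visit. But the date of detection is not the date of fracture. A fracture seen at 6 months may have occurred at any time since implant, so the co-primary outcomes remain informative for that group.
- **Timing of the analysis.** SAP 4.2.1 places the primary analysis when pivotal subjects complete 6 months. With 12 months of expected pivotal enrollment, the longest follow-up is then about 12 + 6 = 18 months, so no scheduled 36-month film would exist. The problem arises only when 4.9.1 is run on data that include later films, and the SAP does not say when it is run or repeated. This limits the point but does not remove it: 4.9.1 is not confined to the pre-market analysis.
- **Document versions.** The fluoroscopy schedule comes from the summary of protocol Revision 6, whereas the SAP cites Revision 2, whose schedule is not available here. The full protocol may say more about fractures.

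It can also be said that the later endpoints will be reported for the whole cohort anyway, and that 4.9.1 does not forbid adding them. Both are true, but SAP 4.4 commits only to descriptive summaries of them, not to a breakdown by fracture.

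**Conclusion.** The point holds in a limited form. For fractures arising after a clean 6-month film, the co-primary outcomes cover at most 1.6% of the days on which the fracture could have occurred, and usually none. Applying the onset rule then pulls that comparison toward no harm. Late fractures are left to device-related adverse events, which may miss a shunt seen only on the core-lab echo.

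This assumes that the Revision 6 fluoroscopy schedule applies, that the 6-month film was done and was clean, and that 4.9.1 is run on data with later films. The bias toward no harm further assumes that the onset rule is applied to co-primary failures.

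How many subjects this affects is unknown. Most of the 36-month follow-up lies after day 180, and a reader might infer that most fractures do too. That would need a constant fracture hazard, and the documents give no data on fracture frequency or timing. Nor do they support a claim that the analysis at the pre-market stage is biased. The change is worth making because it is cheap and alters what the fracture analysis can conclude.

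**What to change.** In SAP 4.9.1:

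1. Add core-lab closure status at 12 and 36 months, and the defined device events through 36 months, each presented by fracture status.
2. Classify each fracture by the film on which it is first seen.
3. Limit the comparison on the 6-month co-primary outcomes to fractures seen by the 6-month film.
4. State that possible timing starts at the last fracture-free film, or at implant if there is none.
5. State at which data cuts the analysis is run.

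The images, readings and endpoint definitions already exist, so the cost is SAP wording and a few more descriptive tables. The long-term part becomes available only after the pre-market analysis, when 36-month data are in. Two limits remain. With timing taken from the last clean film, some events counted against a fracture may in fact have preceded it, and the report should say so. And because follow-up ends at 36 months, no endpoint in this study can show what happens after the 36-month visit.

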3.0 Study Data Collection

3.1 *Study Data Collection Intervals*

Refer to Section 5, Study Procedures and Evaluations, in the study protocol (MD151471).

3.2 *Study Interval Windows*

Subjects with successful study device implant will return for follow-up visits at 30 days, and at 6, 12, and 36 months. For the 24-month assessment, subjects will be contacted by telephone. Subjects considered Technical Failures (study device attempted but not implanted) are only required to complete a 30-day follow-up telephone assessment and will then be discontinued from the study. All intervals are calculated from the index procedure (day 0). The visit windows are calculated as the target day plus or minus the appropriate number of calendar days. The 6-month visit target is 180 days. The yearly visits are calculated on a 365-day year from index procedure.

30 Days	6 Months	12 Months (1 Year)	24 Months (2 Years)	36 Months (3 Years)
30 ± 14 days	180 ± 14 days	365 ± 60 days	730 ± 60 days	1095 ± 60 days

³ Hintze, J. (2013). PASS 12. NCSS, LLC. Kaysville, Utah, USA. www.ncss.com

3.3 *Independent Data Review Board (IDRB)*

Excerpt from section 9.7 of the study protocol:

During the course of the study, the IDRB will serve as both a Data and Safety Monitoring Board (DSMB) and Clinical Events Committee (CEC). As the DSMB, the IDRB will review aggregate safety data for the course of the study to monitor the incidence of SAEs and other safety trends that could warrant modification or termination of the study. As the CEC, the IDRB will adjudicate all site-reported adverse events through 30 days post-procedure for seriousness and relatedness of potential primary endpoint events. In addition, the IDRB will review and adjudicate all site-reported AEs related to arrhythmia for the course of the study. The IDRB Charter will outline the responsibilities and operating procedures of the Board.

3.4 *Site Enrollment Restrictions*

A maximum of 22⁴ investigative sites in the United States will participate in this study. One hundred twenty-five (125) non-training subjects will be enrolled in the Pivotal Phase of this study, with a limit of 10 non-training subjects enrolled at any single site during the Pivotal Phase. The first 2 subjects enrolled at each site will be considered training cases that do not apply to the above restrictions.

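### The AE part of the frame-fracture harm analysis (SAP 4.9.1) counts only device-related AEs, a label with no stated independent or fracture-blind review after day 30 except for arrhythmia

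*SAP*

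**What the plan says.** SAP 4.9.1 names two kinds of outcome for the fracture comparison: "an additional analysis involving co-primary outcomes as well as device-related adverse events will be conducted by stratifying subjects with and without frame fracture". It adds a timing rule for one stratum: "only those events that had an onset date on or following the possible timing of frame fracture will be counted in the frame fracture subgroup". The possible timing is not defined, and no matching rule is given for subjects without fracture.

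On who judges relatedness, SAP 3.3 says that "the IDRB will adjudicate all site-reported adverse events through 30 days post-procedure for seriousness and relatedness of potential primary endpoint events". For later events it makes one exception: "the IDRB will review and adjudicate all site-reported AEs related to arrhythmia for the course of the study". Its other later role is as a monitoring board: "the IDRB will review aggregate safety data for the course of the study".

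SAP 4.5 says "All site-reported AEs will be MedDRA coded" and groups them by "primary relationship (device, procedure, study medication, and unrelated" (among other factors). It does not name the assessor of that relationship.

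The Protocol's Schedule of Events lists "Fluoroscopy (6 months for all Subjects" and then a second follow-up film at 36 months. SAP 3.2 sets the 6-month window at 180 ± 14 days. SAP 3.5 has fluoroscopic images uploaded to the imaging portal, but the core lab evaluations it lists are echocardiographic only.

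**The concern.** There are two problems, and the first does not depend on what anyone knows about the film.

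- **Filtering on attribution.** The analysis asks whether fracture causes harm, but its AE part admits only events that someone has already attributed to the device. An AE caused by a fracture and labelled unrelated is not counted.
- **Labelling with fracture status known.** If whoever sets the label has seen the film, an ambiguous event may be called device-related more readily in a fractured subject, or less readily if the fracture is thought benign. A difference in labelling could then look like harm, or hide it.

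SAP 4.9.1 is the only analysis in the supplied text aimed at fracture harm. Its co-primary outcomes end early: related SAEs at day 30, device events at day 180, closure at the 6-month echo (SAP 2.5.1). Long-term device events are a secondary endpoint (SAP 2.5.2), but 4.9.1 does not name them. Device-related AEs are therefore the only outcome that 4.9.1 names for the period after 6 months.

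**Working it through.** The plan gives no fracture rate, AE rate or labelling rate, so it has no figure to reproduce. The check is timeline arithmetic from the documents, followed by an illustration on assumed inputs.

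**1. Timeline.** Inputs: adjudication to day 30 (SAP 3.3); 6-month visit at 180 ± 14 days and 36-month target at day 1095 (SAP 3.2); follow-up films at 6 and 36 months (Protocol, Schedule of Events).

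- First follow-up film: 180 − 14 = day 166 to 180 + 14 = day 194. That is 136 to 164 days after general adjudication ends.
- Days with no stated independent relatedness review of non-arrhythmia AEs: (1095 − 30)/1095 = 1065/1095 = 97.3%. This is a share of calendar time, not of events.
- Days after the co-primary outcomes' day 180: 1095 − 180 = 915, and 915/1095 = 84%.

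**2. How much of the unadjudicated period follows the film.**

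- To 36 months, film at day 166, 180 or 194: 929/1065 = 87.2%, 915/1065 = 85.9%, 901/1065 = 84.6%.
- To the end of the 6-month window, same film days: 28/164 = 17%, 14/164 = 8.5%, 0/164 = 0%.

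Most labels feeding the 6-month PMA analysis would therefore precede the film, unless they are revised later.

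**3. Illustration of the labelling effect (all inputs assumed).** True AE rates are equal in both strata. Let w be the share of AEs in fractured subjects labelled after the film, q0 the chance of a device-related label when fracture is not known, and q1 that chance when it is known. Then

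apparent ratio = [(1 − w) × q0 + w × q1] / q0.

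With q0 = 0.30 and q1 from 0.20 to 0.60:

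| w | q1 = 0.20 | q1 = 0.40 | q1 = 0.60 |
|---|---|---|---|
| 0.09 (6-month data) | 0.97 | 1.03 | 1.09 |
| 0.86 (data to 36 months) | 0.71 | 1.29 | 1.86 |

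For example, (0.14 × 0.30 + 0.86 × 0.60)/0.30 = 0.558/0.30 = 1.86. The w values assume AEs spread evenly over days, labels set near onset, and a fracture visible at 6 months. For a fracture first seen on the 36-month film, nearly all labels precede the film and w is close to zero.

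**4. What an all-AE row would do.** It removes the attribution filter, but it has two limits.

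- *Dilution.* Assume 50% of subjects have an unrelated AE and fracture independently doubles device-related risk from 5% to 10%. All-AE risk is 1 − 0.50 × 0.90 = 55.0% against 1 − 0.50 × 0.95 = 52.5%, a ratio of 1.05.
- *Unequal windows.* The onset rule shortens counting in the fracture stratum only. With a constant low AE rate and possible timing at day 180, equal true rates give about 915/1095 = 0.84.

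**The case against.** The strongest reply is that the documents are silent rather than wrong. A reader might infer that sites set the label after day 30 and do so with the fracture result in hand. No section says so: SAP 4.5 names no assessor, and nothing says who reads the films for fracture or whether sites receive the reading. The supplied protocol is a summary, SAP 3.3 is an excerpt, and the IDRB Charter is not included, so wider adjudication cannot be fully excluded. This stands. What can be said is that the assessor and the blinding are not stated.

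A reader might also infer that the whole fracture analysis is exposed. It is not. Closure is read by the Echo Core Lab, related SAEs through day 30 are adjudicated by the IDRB, and embolization, removal and reintervention need no relatedness label. Arrhythmia AEs are adjudicated throughout. This also stands.

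Nor do the documents support a headline distortion such as a doubling. In the model above, a ratio of 2.0 needs q1 to be twice q0 and every label to be set after the film (w = 1), which the schedule contradicts.

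Finally, 4.9.1 is an additional analysis with no stated test or decision rule, and it does not affect the co-primary tests. That limits the weight of the point. It does not answer the attribution filter, which operates whatever anyone knows about the film.

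**Conclusion.** The concern holds in limited form. The AE part of 4.9.1 rests on an attribution label alone. After day 30 that label has no stated independent review for non-arrhythmia AEs and no stated blinding to fracture. Fracture-caused AEs labelled unrelated would be missed, and labelling with fracture status known is not prevented.

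The size of the labelling effect is unknown. On the assumed inputs it is slight in the 6-month data (0.97 to 1.09) and could be material to 36 months (0.71 to 1.86), in either direction. The documents do not show that biased labelling will occur. They also give no reason to drop the device-related row, since an all-AE comparison alone could conceal a real effect.

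**What to change.** In SAP 4.9.1:

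1. Report all AEs, all SAEs and MedDRA cardiac-SOC AEs by fracture stratum regardless of attributed relationship, beside the device-related AEs and not in place of them.
2. Count events over a comparable time window in both strata, and define the possible timing of fracture that opens it.
3. Mark the device-related row as having no stated independent adjudication after day 30 except for arrhythmia AEs. If the IDRB Charter already provides later review, cite it instead.

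The cost is SAP wording, a few table rows and the programming of a matched window. The AEs are already collected and coded under SAP 4.5, so no new data or visits are needed. The downside is that the added rows are noisier and dilute a true fracture effect. All AEs also remain site-reported, so the change does not blind reporting, and neither kind of row should be read alone.
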